# A randomized controlled Trial to Compare the Histomorphometric and Clinical Outcomes of Soft Tissue Augmentation at the Time of Lateral Ridge Augmentation Procedures.

### Study Protocol

### 1. Objectives/Specific Aims:

The purpose of this investigator-initiated study is to evaluate the effect of soft tissue autogenous vs allogenic grafts on the soft tissue quantity and quality at the time of Guided Bone Regeneration (GBR) in preparation for endosseous implant placement.

Autogenous Connective Tissue Grafting (CTG) and Acellular Dermal Matrix (ADM) soft tissue grafts are mainly used to alter the quality and quantity of soft tissue.

a) Core objectives of this study are to:

1) To evaluate the quality of soft tissue regenerated with the use of the two available soft tissue grafts via histological analysis.

2) To evaluate whether CTG or ADM influences the outcomes of Guided Bone Regeneration (GBR) procedures.

3) To quantify the soft tissue augmentation achieved by the two available soft tissue grafts by direct clinical measurements after the healing

b) Outcomes will be measured by an evaluation of the following:

- 1) The quality of soft tissue regenerated with the use of the two available soft tissue graft via histological analysis (attachment to bone and keratinization)
- 2) Keratinized tissue width (in mm) measured clinically with a periodontal probe from the implant collar to the mucogingival junction.
- 3) Vertical thickness of soft tissue (in mm) measured clinically with periodontal probe around the implant collar from soft tissue surface to bone contact.
- 4) Volumetric change of soft tissue dimensions around the implant collar evaluated by superimposition of pre- and post-grafting digital intra-oral scan.

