Various surgical techniques have been used to obtain adequate amounts of keratinized tissue around dental implants, including the gingival autograft, apically positioned flap (APF), coronally positioned palatal sliding flap, and acellular dermal matrix graft (ADM). Performing a free gingival graft (FGG) prior to im- plant surgery has been suggested when there is minimal keratinized tissue over the edentulous ridge and APF and FGG can be combined in shallow vestibules with minimal keratinized tissue. A recent systematic review demonstrated that the combination of apically positioned flap and free gingival graft (FGG) is the most successful approach to increase the width of keratinized tissue and deepen the vestibule. However, when comparing the use of epithelialized gingival grafts with free connective tissue grafts, their ability to promote keratinized tissue is similar.

These procedures are usually performed before implant placement or during the exposure of submerged implants, which can extend the healing period and result in patients suffering from pain and discomfort through several surgical stages. In addition, these can be time-consuming procedures in cases that already have good primary implant stability and do not need hard-tissue augmentation.

To our knowledge, the influence of soft tissue augmentation at the time of ridge augmentation procedure has not been tested in socket grafting (ridge preservation) and ridge augmentation (deficient healed site) defects. This study aims at evaluating the effects of soft tissue augmentation using CTG or ADM on the clinical (amount) and histologic (% vital bone) outcomes at time of lateral ridge augmentation.

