### 3. Study Population, Protocol Procedure, and Method:

Approximately 60 adults determined to need ridge augmentation graft of any ethnicity or gender with established UAB School of Dentistry Records may be enrolled in the study.

Participants must be at least 18 years old with demonstrated ability to understand and consent to the proposed study procedure. Decisionally-impaired adults and/or minors who cannot consent for themselves will not be enrolled. Women who report a current pregnancy or patients who are not systemically healthy enough to receive out-patient elective dental care at the time of enrollment will be excluded.

All attending faculty and residents in the UAB Department of Periodontology will be notified of this study. Patients seeking dental implant therapy routinely present to the Periodontal clinic to have a consultation regarding ridge augmentation. Upon completion of the exam by the periodontal resident faculty members will confirm the appropriate treatment plan (bone grafting). If the patient is considered potentially eligible the PI will be asked to explain the study procedures and confirm eligibility based on the clinical and radiographic findings (inclusion criteria). Candidates will be provided an unsigned copy of the consent form to take with them. Participants will be given a minimum of 24 hours to decide upon participation. Upon agreement for study entry patients will be scheduled by the research team for a screening visit, signing of the Informed Consent document and scheduling of the surgical procedure.

**Screening/baseline visit:** Upon enrollment into the study the patient's medical history and electronic records will be reviewed. Clinical examiners will conduct clinical and radiographic review/exams, the data will be used to determine eligibility according to the inclusion criteria. Study visits and objectives will be explained to all participants. IRB approved written informed consent will be obtained from all the participants.

**Surgical visit (Visit 1):** Patients will be randomized like the flip of a coin to one of the three groups listed on the day of surgery. Randomly generated treatment groups will be printed on note cards and placed in sealed envelopes. Envelope will be opened during the visit.

Group 1: Connective tissue graft (CTG) at time of lateral ridge augmentation, or

Group 2: Acellular Dermal Matrix (ADM) at time of lateral ridge augmentation.

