Group 3: Control group (no soft tissue augmentation at time of lateral augmentation)

During bone augmentation procedure, just before suturing the flaps that were reflected, a CTG (Harvested from the patient's palate) or ADM (donor tissue that is FDA approved) will be sutured to the membrane that covered the bone graft.

**Visit 2:** The sutures will be removed after two weeks. Surgical sites (CTG, ADM or Control group) will be evaluated for healing status and postoperative instructions on resuming oral hygiene measures will be instructed to patients. Review medical history and assess for adverse events experience.

**Visit 3:** Six months post-ridge augmentation, For the research purposes a soft tissue biopsy will be taken at the center of the augmented site after elevating the flap using a 2 mm tissue punch. It is noteworthy that this soft tissue specimen would have been typically drilled away (automatically discarded in the suction system) with the initial implant site preparation drill if a biopsy were not planned (regular clinical setting). Hence, the biopsy procedure will not affect in any negative way the likelihood of implant placement. One Soft tissue biopsy per every participant in each group will be harvested from the site that was augmented and each tissue sample will be labelled a unique set of numbers and/or letters.

The soft tissue biopsy will be harvested and fixed in special solution overnight at 4°C. Fixed tissues will be dehydrated through an ethanol gradient, cleared in xylene, and embedded in paraffin. Embedded Tissues will be sagittal sectioned at 7mm thickness and mounted on Superfrost Plus slides (Fisher Scientific, Hampton, NH, USA). Serial sections of biopsy containing epithelia and connective tissue will then be cleared in xylene, rehydrated, and stained with hematoxylin and eosin (H&E) according to

standard protocol. The samples will be store to the laboratory located in the Institute of Oral Health Research at UAB School of Dentistry for the analysis of the tissue samples.

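### Core Objective 2 asks whether CTG or ADM affects guided bone regeneration, but no listed outcome measures bone and the specimen is not shown to contain any

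*Combined protocol and SAP*

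**What the plan says.** - **Objective.** Section 1 gives as core objective 2: "To evaluate whether CTG or ADM influences the outcomes of Guided Bone Regeneration (GBR) procedures". No variable is attached to it.
- **Aim and title.** The study title promises to "Compare the Histomorphometric and Clinical Outcomes of" soft tissue augmentation. The closing paragraph of Section 2 states the aim as the effect of CTG or ADM "on the clinical (amount) and histologic (% vital bone) outcomes at time of lateral ridge augmentation".
- **Outcomes.** Sections 1 and 7 give the same four: soft-tissue quality by histology (attachment to bone, keratinization), keratinized tissue width, vertical soft-tissue thickness, and volumetric change of the soft tissue. In the thickness outcome, bone is only where the probe stops: "around the implant collar from soft tissue surface to bone contact".
- **Bone measurement.** Section 4 defines the deficiency as a ridge width of 5 mm or less, by bone sounding and CBCT. This is an inclusion criterion. Ridge width is not an outcome.
- **Specimen.** Section 3, Visit 3: "a soft tissue biopsy will be taken at the center of the augmented site after elevating the flap using a 2 mm tissue punch", and "One Soft tissue biopsy per every participant in each group will be harvested from the site that was augmented". The sections are described as containing epithelia and connective tissue, stained with H&E. The same paragraph says this tissue would otherwise be lost to the first implant drill. Section 6 refers instead to a biopsy trephine that replaces that drill.
- **Hypothesis and sample size.** Section 7 concerns soft-tissue thickness and attached tissue, CTG against ADM.

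**The concern.** Section 2 says that GBR is done to regain lost bone, so the natural outcome of GBR is bone. The question has substance in this design, because the CTG or ADM "will be sutured to the membrane that covered the bone graft" and a no-graft control arm is available for comparison. Yet the plan names no bone variable, method, time point or analysis.

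Two things are at stake. First, a core objective would go unanswered, or would be answered afterwards from whatever was noted at implant placement. A standard reading that is not taken at six months cannot be reconstructed at analysis. Second, part of outcome 1, and the histological part of the null hypothesis, may rest on a tissue interface that the specimen is not shown to include.

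**Working it through.** **Step 1. Does any listed outcome measure bone?** The plan has no figure for bone to reproduce, so the check is a reading of the four outcomes in Sections 1 and 7.

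| Outcome | What is measured | Role of bone |
|---|---|---|
| 1. Histology | Quality of soft tissue | What the soft tissue attaches to |
| 2. Keratinized tissue width | Implant collar to mucogingival junction | None |
| 3. Vertical thickness | Soft tissue depth | Lower end of the reading |
| 4. Volumetric change | Soft tissue dimensions, by scan superimposition | None stated; no way of separating bone is described |

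Result: 0 of 4 measure bone quantity or quality, so 1 of 3 core objectives has no outcome.

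**Step 2. Could the specimen supply one?** The texts point both ways.
- Against: Sections 3 and 6 both call it a soft tissue biopsy, Section 3 names a tissue punch, and the processing covers only epithelia and connective tissue.
- For: Section 3 says the tissue would otherwise be drilled away, and Section 6 has a trephine in place of the implant drill.

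Whether the specimen reaches bone is therefore unclear. No bone processing or reading is described in either case, so the percentage of vital bone and attachment to bone are not shown to be measurable.

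**Step 3. What precision would an added bone outcome have?** The documents give no ridge-width SD, so results are in SD units.

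The number per arm is not settled by Section 7, so three values are shown: (60 − 6)/3 = 18; 60/3 = 20; and 22 as stated.

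Assumptions: three equal arms, a common SD, one normally distributed baseline covariate, and zero correlation between baseline and Visit 3 width. Residual degrees of freedom are 3n − 4.

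Ignoring baseline imbalance, the half-width is t(0.975, 3n − 4) × √(2/n):
- n = 18: 2.0086 × 0.3333 = 0.67
- n = 20: 2.0032 × 0.3162 = 0.63
- n = 22: 1.9990 × 0.3015 = 0.60

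These are floors. The variance of an adjusted difference is SD² × [2/n + (baseline mean difference)²/Sxx], where Sxx is the pooled within-arm sum of squares of the baseline. The second term averages (2/n)/(3n − 5), so the typical half-width is the floor times √[1 + 1/(3n − 5)]:
- n = 18: 0.67 × √(1 + 1/49) = 0.68
- n = 20: 0.63 × √(1 + 1/55) = 0.64
- n = 22: 0.60 × √(1 + 1/61) = 0.61

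If all six losses fell in one arm of 20, the comparison would be 14 against 20: 2.0086 × √(1/14 + 1/20) = 2.0086 × 0.3485 = 0.70 SD, before any baseline imbalance. A baseline that predicts Visit 3 width would narrow all of these.

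**The case against.** The best defence is that Objective 2 need not mean bone. The purpose statement in Section 1 speaks only of soft tissue, and Sections 2 and 8 describe displaced mucosa, and Section 2 loss of keratinized tissue, as consequences of ridge augmentation. On that reading the soft-tissue outcomes already address part of what follows GBR. This has some force, and it makes removing Objective 2 a legitimate choice. It does not rescue the current text: the aim in Section 2 names vital bone, and a soft-tissue reading would leave Objective 2 largely repeating Objectives 1 and 3.

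A second defence is that the trephine in Section 6 may yield bone. That stands as far as it goes. A reader might infer that the specimen certainly lacks bone and that the percentage of vital bone is impossible to obtain. The documents do not show this; they leave the specimen ambiguous. Nor do they support doubting keratinization because the flap is raised first, since Section 3 says the sections contain epithelia.

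Third, the visit descriptions omit the clinical soft-tissue measures too, so the absence of a scheduled ridge-width reading there proves nothing. The point rests on the outcome lists and on what is said about the specimen.

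Finally, ridge width is an example chosen here. The only bone measure that the protocol itself names as an aim is the percentage of vital bone.

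**Conclusion.** The point holds. Objective 2 has no outcome that measures bone, and neither the percentage of vital bone nor the attachment-to-bone part of outcome 1 is shown to be measurable. It should be fixed, but it does not threaten the trial's main comparison: a reader might infer that the soft-tissue results are compromised, yet the sized thickness comparison and the clinical soft-tissue outcomes do not depend on it.

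The size is 1 of 3 core objectives without an outcome, and 1 of the 2 histological features in outcome 1 not shown to be in the specimen. An added ridge-width outcome would give half-widths of about 0.61 to 0.68 SD under the assumptions in the working. A reader might take these as upper limits; they are not, since chance imbalance and unequal arms widen them. They describe what the proposed remedy could deliver and do not measure the defect. Intervals this wide support an estimate and cannot establish that the grafts have no influence on bone.

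The tissue punch in Section 3 and the trephine in Section 6 are a separate inconsistency, which bears on the risk statement.

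**What to change.** 1. **Add one secondary bone outcome, or remove Objective 2.** For example, ridge width by one method at both time points, at one site per patient named in advance (Section 4 allows more than one missing tooth), and at a position set from a stable landmark recorded at Visit 1. Section 3 says only "Envelope will be opened during the visit"; take the first reading before that moment, and the second at Visit 3. Analyse Visit 3 width by arm, adjusted for Visit 1 width. Report CTG-control and ADM-control differences with 95% CIs as estimates, not as proof of no influence.
2. **Align the histology.** Remove the percentage of vital bone from the aim, and restrict outcome 1 and the histological part of the null hypothesis to features the specimen shows. The alternative is to state that a specimen already being taken includes bone, and how that bone is processed and read.
3. **Separately, reconcile Sections 3 and 6** on the biopsy instrument, state where the specimen lies relative to the flap, and align the risk statement with the result.

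Cost: wording, plus two short readings. If these are made directly at the two surgeries already planned, no visit, biopsy or imaging is added. Downsides: the position must be found again after six months on an altered ridge, so relocation error will add to the SD, and the Visit 3 reading has no stated masking. If the specimen route is chosen for bone, processing and histomorphometric reading are a further cost. Removing Objective 2 costs wording only.

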#### 2. Background

Dental rehabilitation of partially or totally edentulous patients with oral implants has become a routine treatment modality in the last decades, with reliable long-term results. Early loss of the teeth due to trauma or periodontitis often leads to deformities in these resulting edentulous ridges. Studies have demonstrated that bone resorption will occur secondary to tooth extraction. This tends to occur over a 12-month period, most notably in the first 4 months following extraction.

When a tooth or a group of teeth has been missing for a long time, the patient may present with a ridge that is deficient in thickness and/or height and inadequate for dental implant placement. In these cases, ridge augmentation using guided bone regeneration (GBR) is routinely used to regain the lost bone.

The concept of GBR is based upon the use of a barrier membrane to exclude rapidly growing soft tissue cells from a bony defect and, more importantly, to maintain a space for the slower process of bone formation. Bone grafts or bone substitutes are commonly used in GBR procedures to provide support for the barrier membrane, for additional space maintenance, and/or for their bone healing properties.

An important factor is flap closure during bone augmentation. The key to achieving wound closure is not only the clinician's ability to obtain tension-free release flap but also good soft tissue quality and quantity. In an attempt to achieve wound closure and hence graft stability, the buccal mucosa is often broadly released, and this often results in a severe apical translocation of the mucogingival line, loss of vestibule, and keratinized mucosa (KM). When the vestibule becomes shallow, it often leads to an esthetic challenge as well as a phonetics problem. Moreover, research has shown that areas with minimal KM often have a higher peri-implant plaque accumulation, inflammation, and attachment loss.

Various surgical techniques have been used to obtain adequate amounts of keratinized tissue around dental implants, including the gingival autograft, apically positioned flap (APF), coronally positioned palatal sliding flap, and acellular dermal matrix graft (ADM). Performing a free gingival graft (FGG) prior to im- plant surgery has been suggested when there is minimal keratinized tissue over the edentulous ridge and APF and FGG can be combined in shallow vestibules with minimal keratinized tissue. A recent systematic review demonstrated that the combination of apically positioned flap and free gingival graft (FGG) is the most successful approach to increase the width of keratinized tissue and deepen the vestibule. However, when comparing the use of epithelialized gingival grafts with free connective tissue grafts, their ability to promote keratinized tissue is similar.

These procedures are usually performed before implant placement or during the exposure of submerged implants, which can extend the healing period and result in patients suffering from pain and discomfort through several surgical stages. In addition, these can be time-consuming procedures in cases that already have good primary implant stability and do not need hard-tissue augmentation.

To our knowledge, the influence of soft tissue augmentation at the time of ridge augmentation procedure has not been tested in socket grafting (ridge preservation) and ridge augmentation (deficient healed site) defects. This study aims at evaluating the effects of soft tissue augmentation using CTG or ADM on the clinical (amount) and histologic (% vital bone) outcomes at time of lateral ridge augmentation.

### 3. Study Population, Protocol Procedure, and Method:

Approximately 60 adults determined to need ridge augmentation graft of any ethnicity or gender with established UAB School of Dentistry Records may be enrolled in the study.

Participants must be at least 18 years old with demonstrated ability to understand and consent to the proposed study procedure. Decisionally-impaired adults and/or minors who cannot consent for themselves will not be enrolled. Women who report a current pregnancy or patients who are not systemically healthy enough to receive out-patient elective dental care at the time of enrollment will be excluded.

All attending faculty and residents in the UAB Department of Periodontology will be notified of this study. Patients seeking dental implant therapy routinely present to the Periodontal clinic to have a consultation regarding ridge augmentation. Upon completion of the exam by the periodontal resident faculty members will confirm the appropriate treatment plan (bone grafting). If the patient is considered potentially eligible the PI will be asked to explain the study procedures and confirm eligibility based on the clinical and radiographic findings (inclusion criteria). Candidates will be provided an unsigned copy of the consent form to take with them. Participants will be given a minimum of 24 hours to decide upon participation. Upon agreement for study entry patients will be scheduled by the research team for a screening visit, signing of the Informed Consent document and scheduling of the surgical procedure.

**Screening/baseline visit:** Upon enrollment into the study the patient's medical history and electronic records will be reviewed. Clinical examiners will conduct clinical and radiographic review/exams, the data will be used to determine eligibility according to the inclusion criteria. Study visits and objectives will be explained to all participants. IRB approved written informed consent will be obtained from all the participants.

**Surgical visit (Visit 1):** Patients will be randomized like the flip of a coin to one of the three groups listed on the day of surgery. Randomly generated treatment groups will be printed on note cards and placed in sealed envelopes. Envelope will be opened during the visit.

Group 1: Connective tissue graft (CTG) at time of lateral ridge augmentation, or

Group 2: Acellular Dermal Matrix (ADM) at time of lateral ridge augmentation.

Group 3: Control group (no soft tissue augmentation at time of lateral augmentation)

During bone augmentation procedure, just before suturing the flaps that were reflected, a CTG (Harvested from the patient's palate) or ADM (donor tissue that is FDA approved) will be sutured to the membrane that covered the bone graft.

**Visit 2:** The sutures will be removed after two weeks. Surgical sites (CTG, ADM or Control group) will be evaluated for healing status and postoperative instructions on resuming oral hygiene measures will be instructed to patients. Review medical history and assess for adverse events experience.

**Visit 3:** Six months post-ridge augmentation, For the research purposes a soft tissue biopsy will be taken at the center of the augmented site after elevating the flap using a 2 mm tissue punch. It is noteworthy that this soft tissue specimen would have been typically drilled away (automatically discarded in the suction system) with the initial implant site preparation drill if a biopsy were not planned (regular clinical setting). Hence, the biopsy procedure will not affect in any negative way the likelihood of implant placement. One Soft tissue biopsy per every participant in each group will be harvested from the site that was augmented and each tissue sample will be labelled a unique set of numbers and/or letters.

The soft tissue biopsy will be harvested and fixed in special solution overnight at 4°C. Fixed tissues will be dehydrated through an ethanol gradient, cleared in xylene, and embedded in paraffin. Embedded Tissues will be sagittal sectioned at 7mm thickness and mounted on Superfrost Plus slides (Fisher Scientific, Hampton, NH, USA). Serial sections of biopsy containing epithelia and connective tissue will then be cleared in xylene, rehydrated, and stained with hematoxylin and eosin (H&E) according to

standard protocol. The samples will be store to the laboratory located in the Institute of Oral Health Research at UAB School of Dentistry for the analysis of the tissue samples.

